5.6 Follow-up of subjects withdrawn from treatment

Subjects who withdraw from the study or who terminate the recording session prematurely, in the absence of any adverse event, will not be followed.

5.7 Premature termination of the study

Serious adverse events are not expected, but in case they do occur, the research group can decide to premature terminate the study.

6. SAFETY REPORTING

6.1 Section 10 WMO event

In accordance to section 10, subsection 4, of the WMO, the sponsor will suspend the study if there is sufficient ground that continuation of the study will jeopardize subject health or safety. The sponsor will notify the accredited METC without undue delay of a temporary halt including the reason for such an action. The study will be suspended pending a further positive decision by the accredited METC. The investigator will take care that all subjects are kept informed.

6.2 Adverse and serious adverse events

Adverse events are defined as any undesirable experience occurring to a subject during the study, whether or not considered related to the surgery or audiological follow-up. Up to three days after the last test, all adverse events reported spontaneously by the subject or observed by the investigator or his staff will be recorded.

A serious adverse event is any untoward medical occurrence or effect that at any dose:

- results in death;
- is life threatening (at the time of the event);
- requires hospitalisation or prolongation of existing patients' hospitalisation;
- results in persistent or significant disability or incapacity;
 - is a congenital anomaly or birth defect; or
 - any other important medical event that did not result in any of the outcomes listed above due to medical or surgical intervention but could have been based upon appropriate judgement by the investigator.

An elective hospital admission will not be considered as a serious adverse event

All SAEs will be reported through the web portal *ToetsingOnline* to the accredited METC that approved the protocol, within 15 days after the sponsor has first knowledge of the serious adverse reactions.

SAEs that result in death or are life threatening should be reported expedited. The expedited reporting will occur not later than 7 days after the responsible investigator has first knowledge of the adverse reaction. This is for a preliminary report with another 8 days for completion of the report.

6.3 Follow-up of adverse events

All adverse events will be followed until they have abated, or until a stable situation has been reached. Depending on the event, follow up may require additional tests or medical procedures as indicated, and/or referral to the general physician or a medical specialist.

7. STATISTICAL ANALYSIS

7.1 Descriptive statistics

We will use an ANOVA test to compare the primary outcome measure hearing preservation (see 5.3) between the four groups. We will do the same for the CVC word score tests (with and without noise) between the groups.

Fisher's exact test of independence will be used to compare the electrode location within the scala tympani (correct location after insertion) between CO or RW approach, and between PM or LW electrode insertion.

We will also use multiple regression analysis to identify independent predictors of hearing preservation. Among the factors to examine are insertion depth and cochlear volume.

We will use a Pearson correlation test to examine the correlations between the ECochG responses and hearing preservation at the various time points (during and after cochlear implantation)..

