Rationale: In order to preserve the residual hearing in patients with sensorineural hearing loss (SNHL) receiving a cochlear implant (CI), the insertion trauma to the delicate and microscopic structures of the cochlea needs to be minimized. The surgical procedure starts with the conventional mastoidectomy-posterior tympanotomy (MPT) approach to the middle ear, and is followed by accessing the cochlea, with either a cochleostomy (CO) or via the round window (RW). Both techniques have their benefits and disadvantages. Another aspect is the design of the electrode array. There are fundamentally two different designs: a 'straight' lateral wall lying electrode array (LW), or a 'pre-curved' perimodiolar cochlear lying electrode array (PM). Interestingly, until now, the best surgical approach and type of implant is unknown. Our hypothesis is that the combination of a RW approach and a LW lying electrode array minimizes insertion trauma, leading to better hearing outcome for SNHL patients.

Objective: Comparison of hearing preservation and outcome of two fundamentally different cochlear implants designs (LW or PM) and the two most used surgical approaches (RW or CO). Secondly, asses the structure preservation (i.e., scalar position) of each combination of electrode design/surgical approach. Thirdly, find objective electrophysiological measures for insertion trauma.

Study population: A total of 48 patients with severe SNHL, age ≥ 18 years, who meet the in/exclusion criteria used for cochlear implantation.

Study design: Randomized controlled single-blind trial consisting of four groups: 1: RW and LW, 2: CO and LW, 3: RW and PM and 4: CO and PM.

Intervention: Randomization to one of the four groups.

Main study parameters/endpoints: Primary outcome: Pre- and postoperative hearing thresholds of (low frequency) pure tone audiometry (LF-PTA), secondary outcomes: scalar position of the electrode array, ECochG measures and speech perception score.

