3. STUDY DESIGN

The study design is illustrated in **figure 3**:

This study concerns a single-blind mono-center randomized controlled, with 18 year and older severely or profoundly hearing-impaired patients who are eligible for a cochlear implant. Every candidate for cochlear implantation needs to have severe hearing loss bilaterally, should not have contraindications for surgery and should be able to follow an intensive medical rehabilitation program. The study will be performed at the department of Otorhinolaryngology in the University Medical Center Utrecht, and will run till 01-01-2027.

[figure not shown]
All participants will undergo the usual standard medical care of work-up before cochlear implantation. The work-up includes a pure tone audiogram (PTA), a speech audiogram, a preoperative CT, and interviews with speech therapist, audiologist, ENT surgeon and social worker. In a multidisciplinary meeting, the Cochlear implantation team of the UMC Utrecht will assess all results and decides whether a patient is suited for a cochlear implant.

Eligible cochlear implant candidates will then for this study be randomized to group 1 (RW + LW), 2 (CO + LW), 3 (RW + PM) or group 4 (CO + PM).

Study procedures:

For all patients, during implantation, the standard measurements for eCAP and electrode impedances and the experimental measurements of ECochG will be performed. Postoperatively, a cone beam CT scan will be made to assess the scalar position of the CI. After activation of the CI, which is usually around three to four weeks postoperatively, the ECochG measurements will be repeated. For this study, we add two extra pure tone audiograms at 6 /12 months, resulting in a total of 4 audiograms (at one three, six and 12 months). Pure tone audiometry is without CI, which will allow us to determine the residual acoustic hearing capability of the patients. At 12 months, a conventional speech perception test with consonant-vowel-consonant (CVC) word score with/without noise will be performed. The speech perception test is with CI and determines the maximal electrical hearing capability of the patients. Finally, at 12 months, we will add a spectral ripple test, allowing us to measure hearing performance independent of cognitive and linguistic skills (Drennan et al., 2014).

Study Design

Light grey: Standard medical care

Dark grey: Extra for study

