4.4 Sample size calculation

Hearing preservation is the main outcome variable (see further 5.1). Based on literature (Manjaly et al., 2018; Rader et al., 2018; Sierra et al., 2019) we expect a large range of hearing preservation for each group, from 0 (no preservation, i.e., loss of all hearing) to 100 (full preservation, hearing stable), and occasionally above (improved hearing). The three studies showed means of 56, 74, and 53, respectively and within-group standard deviations, σ_w , of 37, 19 and 37. Weighing the larger studies more (Manjaly, Sierra) we estimate $\sigma_w = 35$ group means of 50 with clinically interesting differences of 40 between best and worst group means. This yields a variance between groups of 400, i.e., $\sigma_B = \sqrt{400} = 20$ (σ_B : standard deviation between groups). Thus, effect size $\sigma_B / \sigma_w = 0.57$. Using a group size of 12 yields a robust power of 0.9. We used G*power (version 3.1.9) to calculate the power based on effect size and sample size with a one-way ANOVA test, with fixed effects.

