5. METHODS

5.1 Study parameters/endpoints

5.1.1 Main study parameter/endpoint

Hearing preservation is the main outcome, which will be expressed in percentage. Hearing preservation is calculated by the following formula: $HP = 1 - (PTA\ post - PTA\ pre) / (PTA\ max - PTA\ pre)$. See section 5.3.

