5.3 Study procedures

For this study there are procedures before, during or after the cochlear implantation surgery, or pre, intra and post-operatively respectively.

Preoperatively (standard medical care): Before randomization, each participant will undertake the normal standard preoperative work-up: a CT scan, a pure tone audiogram/speech test and interviews with ENT specialist and audiologist.

Intraoperatively: all participants will undergo, according to the group they are allocated to, either a CO or RW insertion approach and receive either the PM or the LW electrode array. During and right after cochlear insertion, ECochG potentials will be recorded to study possible insertion trauma. The surgical procedures are standard medical care.

Postoperatively: all patients will receive a cone beam CT scan, to assess the scalar localization of the electrode. Upon activation of the CI, around 3-4 weeks after surgery, the first postoperative PTA/ECochG will be measured. In the following months, the PTA/ECochG is

repeated at 3, 6 and 12 months after surgery. At one year after surgery, the clinical ripple test and the standard CVC word tests with and without noise will be performed to study the eventual hearing outcome for each group. See **study design diagram** for an overview.

1. Hearing preservation

Preoperative pure tone audiometry is already a standard test to assess the eligibility for a cochlear implant for severe hearing impaired patients. With postoperative pure tone audiometry (without CI) we can calculate the hearing preservation by the following equation:

$$HP = 1 - (PTA\ post - PTA\ pre) / (PTA\ max - PTA\ pre)$$

In this equation, HP is Hearing preservation, PTA_{pre} is the average pure-tone (unaided) hearing threshold of 125, 250 and 500 Hz measured preoperatively, PTA_{post} is the same average pure-tone hearing threshold measured postoperatively, and PTA max is the maximum sound intensity generated by a standard audiometer (usually between 90-120 dB HL) (Skarzynska et al., 2018).

2. Scalar positioning of the electrode array

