One year after cochlear implantation, a conventional speech perception test with/without noise test will be performed with CVC words from the 'Nederlandse Vereniging voor Audiologie' (NVA) word-list. The speech tests can be quantified with a simple correct percentage score. Also, the clinical ripple test, which uses tones instead of words, can be used to complement speech perception scores (Drennan et al., 2014).

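### The primary hearing preservation endpoint is not tied to any one of the four planned postoperative audiograms

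*Protocol*

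**What the plan says.** Section 7.1 plans a single primary test: "We will use an ANOVA test to compare the primary outcome measure hearing preservation (see 5.3) between the four groups". Section 4.4 also points elsewhere for the definition: "Hearing preservation is the main outcome variable (see further 5.1". Section 5.1.1 states "Hearing preservation is the main outcome, which will be expressed in percentage", gives the formula HP = 1 − (PTA post − PTA pre)/(PTA max − PTA pre), and refers on to 5.3. There PTA pre is the mean unaided threshold at 125, 250 and 500 Hz before surgery, and PTA post "is the same average pure-tone hearing threshold measured postoperatively".

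Several postoperative audiograms fit that description. Section 3 counts them: "resulting in a total of 4 audiograms (at one three, six and 12 months". Section 5.3 places the first at activation, about 3 to 4 weeks after surgery, and has it "repeated at 3, 6 and 12 months after surgery".

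The Summary gives the primary outcome as "Pre- and postoperative hearing thresholds of (low frequency) pure tone audiometry (LF-PTA", again without a visit, and the primary objective in section 2 names none. The speech test, by contrast, is dated: "One year after cochlear implantation, a conventional speech perception test with/without noise test will be performed".

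On the model, section 5.2 stratifies randomisation by age (18-50 and over 50 years). Section 4.4 sizes the comparison as a one-way fixed-effects ANOVA, and 7.1 names no model term other than group.

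**The concern.** The assessment time is part of what an endpoint is. Following the cross-references from 7.1 or from 4.4 leads through 5.1.1 to 5.3 and stops at a threshold that could be any of four. Nothing in the text rules out running the ANOVA at each visit and then deciding which one answers the primary objective. Residual hearing may change over the first year, so the four answers need not agree. Even without any selection, a reader could not tell which result is the primary one. The same gap reaches the sample size: the SD of 35 and the 40-point difference are tied to no follow-up time.

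The smaller matter is that the comparison as sized leaves out the factor on which randomisation is stratified. This affects precision only.

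**Working it through.** **1. The protocol's own power.** Inputs from section 4.4: 12 per group (N = 48), between-group SD 20, within-group SD 35. Alpha is not stated; 0.05 is assumed.
- f = 20/35 = 0.571 (the protocol gives 0.57).
- Noncentrality = N × f² = 48 × 0.3265 = 15.67, with 3 and 44 degrees of freedom.
- Power from the noncentral F distribution = 0.903. The stated 0.9 reproduces. At alpha 0.025 or 0.10 the power would be 0.840 or 0.950, so 0.05 is the level that fits.

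**2. Where a visit could have been named.**

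| Place in protocol | Visit for primary HP |
|---|---|
| Summary, primary outcome | none |
| Section 2, primary objective | none |
| Section 4.4 | none; refers to 5.1 |
| Section 5.1.1 | none; refers to 5.3 |
| Section 5.3, definition of PTA post | none |
| Section 7.1 | none; refers to 5.3 |

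**3. What the open visit could do.** The protocol gives no between-visit correlations, so these are assumed. Trials of 4 groups × 12 patients with four correlated visits were simulated, and each visit was tested with F(3, 44) at 0.05. *Equal* means the same correlation between every pair of visits. *Decaying* means the correlation raised to the power of the distance between visits. The effect in the last two columns is the protocol's f = 20/35, assumed the same at every visit. *Disagree* means at least one visit is significant, but not all four.

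| Correlation | Any visit significant, no effect: equal | decaying | Visits disagree, protocol's effect: equal | decaying |
|---|---|---|---|---|
| 0.7 | 0.14 | 0.15 | 20% | 23% |
| 0.8 | 0.12 | 0.14 | 16% | 19% |
| 0.9 | 0.10 | 0.11 | 12% | 14% |

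Repeat simulations agree to within about one percentage point. For reference, four independent tests would give 1 − 0.95⁴ = 0.185.

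**4. Age stratum.** Suppose age shifts HP by an assumed 0.25, 0.5 or 1.0 SD, with exact balance across groups and 25% to 50% of patients in one stratum. Leaving the stratum out moves its variation into the error term, which becomes a noncentral chi-square on 44 df with noncentrality 48 × p(1 − p) × shift². The true level of the nominal 0.05 test is then:
- shift 0.25 SD: 0.048 to 0.047
- shift 0.5 SD: 0.042 to 0.040
- shift 1.0 SD: 0.026 to 0.021

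The error is in the conservative direction. Including the stratum costs one error degree of freedom (44 to 43). If age explains nothing and is balanced, power with the same noncentrality of 15.67 is still 0.903.

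**5. Preoperative threshold as a covariate.** PTA pre is in both the numerator and the denominator of HP. With PTA max = 120 dB, a 10 dB loss gives HP = 1 − 10/(120 − PTA pre):
- PTA pre 40: 1 − 10/80 = 88%
- PTA pre 60: 1 − 10/60 = 83%
- PTA pre 80: 1 − 10/40 = 75%
- PTA pre 100: 1 − 10/20 = 50%

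The same loss in dB therefore acts on HP nonlinearly in PTA pre, which a single additive linear term does not capture.

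**The case against.** **Twelve months is implied.** The one-year mark belongs to the speech and ripple tests and to the secondary objective on performance with the implant. Section 3 separates these from the audiogram, which is made without the implant to measure residual acoustic hearing. The date does not carry over.

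**All visits will be analysed together.** Section 2 lists residual hearing over time as a separate secondary objective, 7.1 speaks of several time points only for the ECochG correlations, and no repeated-measures model is described.

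**The analysis plan may settle it.** This is a fair defence for covariates: 7.1 neither lists nor excludes model terms, one-way appears only in the sizing, and the separate regression in 7.1 has an open list of predictors. The missing age stratum is therefore no error. The defence is weak for the visit, because the protocol has a section for the primary endpoint, fixes its formula and frequencies there and in 5.3, and dates the speech tests.

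**The error rates are a worst case.** This stands. They require someone to run four tests and claim on any one, whereas the protocol plans one. The correlations and the constant effect are assumptions. A reader might infer that this trial's type I error is 0.10 to 0.15; the document does not support that.

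**Figure 3 is not shown.** Its caption describes a flow chart of procedures, so it probably does not name the primary visit, but this could not be checked.

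**Conclusion.** The point holds for the endpoint definition: the readable text leaves the primary HP open among four visits, so the primary result is not uniquely defined. Its size can only be illustrated. Under assumed correlations of 0.7 to 0.9, a claim on the best of four visits would give a false-positive rate of about 0.10 to 0.15, and the visits would disagree in about 12 to 23% of trials under the planned effect.

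Three stronger readings are not supported:
- **That the sample size is wrong on this account.** The power of 0.9 reproduces, and naming a visit does not alter it if the SD of 35 and the 40-point difference apply there.
- **That the unadjusted ANOVA is biased or invalid.** Randomisation protects it. Omitting the stratum makes it only slightly conservative for age effects up to about 0.5 SD, and more so only if age were as strong as 1 SD.
- **That the primary model must adjust for the preoperative low-frequency threshold.** HP is already scaled by it. Any power gain from such a covariate rests on an assumed share of explained variance, not on HP built from its formula.

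**What to change.** Before outcome data are seen:
- **Section 5.1.1:** name one visit for the primary HP. Twelve months is one option, since it matches the speech tests. Label HP at the other visits secondary, under the objective on residual hearing over time.
- **Section 4.4:** state that the SD of 35 and the 40-point difference are assumed at that visit.
- **Section 7.1:** say that the ANOVA uses HP at that visit and, for precision only, include the age stratum (18-50, over 50) alongside the four groups.
- **Preoperative low-frequency threshold:** do not require it as a linear covariate in the primary model; at most use it in a sensitivity analysis.

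The cost is a few sentences and one error degree of freedom, with no new data and no extra patients. N = 48 and power of 0.90 stand under the planning assumptions. Keeping all four visits as co-primary with a Bonferroni correction would be dearer: at 0.05/4 = 0.0125 per visit, the power at each visit falls to 0.76.

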5.2 Randomisation, blinding and treatment allocation

Patients will be randomly allocated to one of four groups. Block randomization will take place electronically by the study management system researchtool. The Julius Center will handle this randomization procedure. All groups carry the same equal weight. They will stratify the groups for age, with two subgroups, 18-50 years and > 50 years. This study is single-blind, meaning that only participants are blinded for the treatment allocation. However, research assistants will be blinded for the treatment.

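### The 12-month CVC scores are compared by unadjusted ANOVA although randomisation is stratified by age and a preoperative speech test exists; the test is valid but possibly conservative, with a gain from adjustment that the protocol does not let one size

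*Protocol*

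**What the plan says.** Section 7.1 sets the primary analysis: "We will use an ANOVA test to compare the primary outcome measure hearing preservation (see 5.3) between the four groups". The next sentence carries the method over to speech: "We will do the same for the CVC word score tests (with and without noise) between the groups". The only model with covariates in that section is for a different outcome: "We will also use multiple regression analysis to identify independent predictors of hearing preservation".

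On randomisation, section 5.2 states: "They will stratify the groups for age, with two subgroups, 18-50 years and > 50 years".

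On what is measured before surgery, section 5.3 says that before randomisation "each participant will undertake the normal standard preoperative work-up: a CT scan, a pure tone audiogram/speech test". Section 3 agrees: "The work-up includes a pure tone audiogram (PTA), a speech audiogram, a preoperative CT". Neither place names the speech material, a noise condition, aided or unaided listening, or a score per ear.

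On the 12-month test, section 3 says: "The speech perception test is with CI and determines the maximal electrical hearing capability of the patients". Section 5.1.2 lists the CVC score, in per cent, among the secondary endpoints.

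**The concern.** The protocol does not leave the CVC method open. It names a test, and that test uses neither the one factor balanced by design nor a speech measure taken on every patient beforehand.

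Two consequences follow if those variables predict the 12-month score. First, stratifying by age makes the group means vary less from trial to trial than under simple randomisation. An ANOVA that ignores age keeps the age variance in its error term, so its standard errors are too large and the test rejects too rarely. Second, whatever variance the preoperative score explains also stays in the error term. With 12 patients per group, that could matter for the comparison of speech between arrays and approaches.

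**Working it through.** **Inputs from the protocol.** Four groups with equal allocation (section 5.2); 12 per group, N = 48, within-group SD 35, between-group SD 20, stated power 0.9, one-way fixed-effects ANOVA (section 4.4). These figures concern hearing preservation. Nothing comparable is given for CVC.

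**Assumed.** Two-sided α = 0.05 (not stated in section 4.4). CVC effect size f = 0.571 (borrowed) or f = 0.40 (a smaller effect). Combined within-group correlation ρ of the two covariates with the CVC score: 0 to 0.5, with R² = ρ².

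**Step 1: reproduce the stated power.** f = 20/35 = 0.571. Noncentrality λ = N·f² = 48 × 0.3265 = 15.67. With 3 and 44 degrees of freedom, power is 0.903, which matches the stated 0.9. At f = 0.40, λ = 48 × 0.16 = 7.68 and power is 0.592. These are the unadjusted reference values.

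**Step 2: adjust for two covariates.** Residual variance is multiplied by (1 − ρ²). Estimating two covariates that may be unbalanced across groups costs a factor of about 1 + 2/41 = 1.049. So f becomes f/√[(1 − ρ²)(1 + 2/41)], with 3 and 42 degrees of freedom.

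| ρ | R² | Net variance | Power, f = 0.571 | Change | Power, f = 0.40 | Change |
|---|---|---|---|---|---|---|
| unadjusted | – | 1 | 0.903 | – | 0.592 | – |
| 0 | 0 | 1.049 | 0.887 | −2 | 0.567 | −2 |
| 0.2 | 0.04 | 1.007 | 0.900 | 0 | 0.586 | −1 |
| 0.3 | 0.09 | 0.954 | 0.916 | +1 | 0.612 | +2 |
| 0.4 | 0.16 | 0.881 | 0.937 | +3 | 0.651 | +6 |
| 0.5 | 0.25 | 0.787 | 0.960 | +6 | 0.706 | +11 |

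Changes are in percentage points, rounded.

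**Step 3: break-even.** Net variance equals 1 when (1 − R²)(43/41) = 1, so R² = 1 − 41/43 = 0.047, or ρ about 0.22. Below that, adjusting for both covariates slightly widens the intervals.

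**Step 4: age stratum alone.** If stratification balances age exactly, the factor 1 + 2/41 does not apply and only one degree of freedom is spent (3 and 43). With f/√(1 − R²), R² = 0 gives power 0.903 and 0.591, practically the unadjusted values. R² = 0.09 gives 0.930 and 0.636. Real balance will be approximate, so the true cost is slightly above zero.

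**Step 5: direction of the error when age is left out.** Simulation used 4,000 trials per setting under no group effect, with age balanced exactly across arms, an assumed one-third/two-thirds split and an age correlation of 0.3. Plain ANOVA rejected in about 3.5% of trials and the adjusted model in about 4.8%. Omitting a prognostic stratum therefore makes the ANOVA conservative, not too liberal.

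**The case against.** The case for leaving section 7.1 alone has weight. ANOVA is a correct test for four randomised groups, CVC is a secondary endpoint, and covariates for such endpoints are often set in a statistical analysis plan, which is not shown here. That lowers the importance but does not remove the point. Section 7.1 names the method, so a later plan that adjusts would depart from it.

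The preoperative score is a weaker covariate than it looks. A reader might infer that it is the CVC endpoint's own baseline. The protocol does not support that: no CVC material, noise condition or ear is stated for it, and the later test is done with the implant while the earlier one precedes it. An adjusted model does not need the same instrument, because it estimates the slope. A weak correlation would still make the adjustment worthless. Section 4.1 describes severe to profound bilateral loss, so preoperative scores near the floor are plausible.

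A reader might also infer that precision is certainly lost, or that chance imbalance biases the comparison. Neither follows. The loss depends on an R² that the protocol does not give. Randomisation keeps the comparison unbiased, and the ANOVA error term already carries the chance variation.

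The age stratum largely escapes these objections, since it is recorded for everyone and balanced by design.

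**Conclusion.** The point holds as a modest improvement to a stated method. The planned CVC comparison is valid, but it is conservative if age predicts the score and may be less precise than the data allow. The size cannot be fixed from the protocol. For an assumed ρ of 0.3 to 0.5, the gain is about 1 to 6 power points at f = 0.571 and 2 to 11 at f = 0.40. The loss is about 2 points if both covariates are unrelated to the outcome. These figures rest on an effect size borrowed from hearing preservation or assumed, on α = 0.05, and on an approximate cost factor that is on the high side for a stratified variable.

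The age stratum is the firm part, because including it is close to free. The preoperative score is conditional on what is actually recorded. The conclusion covers the CVC scores only. It does not show that the speech comparison is biased or invalid, and it says nothing about the hearing preservation model.

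**What to change.** In section 7.1, replace the sentence on the CVC tests with wording such as: *The 12-month CVC scores, with and without noise, will each be compared between the four groups by a linear model with randomised group and the age stratum (18–50, >50). The preoperative speech score will be added as a continuous covariate if a comparable score is recorded for all participants and is not mostly at the floor; this will be decided and documented before any outcome data are seen.* The protocol should also state which preoperative score is meant: material, ear, and listening condition.

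Cost: one or two of the 44 residual degrees of freedom, no new data collection, and a slight loss of power (about 2 points with both covariates) if they turn out not to be prognostic.
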